# 5.7. PATIENT WITHDRAWAL CRITERIA

In accordance with the Declaration of Helsinki, patients will be free to withdraw from the study at any time if they wish to do so, for any reason specified or unspecified. Such withdrawal should not affect the required and provided medical care.

In addition, the Investigator may interrupt the patient participation from the study at any time if he/she considers it necessary for any reason including:

- Pregnancy.
- Ineligibility (either arising during the study or retrospective having been overlooked at screening).
- Significant protocol deviation.
- Significant non-compliance with treatment regimen or study requirements.
- An AE which requires discontinuation of the study medication or results in inability to continue to comply with study procedures, particularly if the patient presents a **severe depression** (BDI-21 item total score ≥30), or **suicidal ideation or behavior** (BDI-21 Item #9 >0 and active suicidal ideation in C-SSRS), or **severe hypotension** (SPB/DBP <90/60 mmHg), or **orthostatic hypotension** as defined by the ESH, or **sustained un-tolerated bradycardia** (HR <50 bpm).
- Consent withdrawn.
- Lost to follow-up.
- The Investigator or Sponsor determines it is in the best interest of the subject to discontinue the patient's participation in the study.

Patients who discontinue study treatment or active participation in the study will no longer receive study treatment but will be followed for safety. When a patient withdraws from the study, the reason(s) for withdrawal shall be recorded by the Investigator on the relevant page of the eCRF. Whenever possible, all patients who discontinue study treatment or withdraw from the study prematurely will undergo all end-of-treatment assessments. Patients who fail to return for final assessments will be contacted by the site staff. Following a minimum of 2 documented unsuccessful telephone calls, a registered letter will be sent to the patient in a final attempt to ensure protocol compliance.

It is vital to obtain follow-up data on any patient withdrawn because of an AE or SAE. In every case, efforts must be made to undertake protocol-specified, safety, follow-up procedures.

## 5.8. STUDY DISCONTINUATION

# 5.8.1. Criteria for terminating the trial

The Sponsor reserves the right to terminate the study but intends only to exercise this right for valid scientific or administrative reasons, and reasons related to protection of patients. In all cases the Ethic Committees (IRB/IEC) and Health Authorities should be informed. Possible reason for the study termination can include but are not limited to:

- The discovery of an unexpected, significant or unacceptable risk to patients enrolled in the study.
- A decision on the part of the Sponsor to suspend or discontinue the development of the investigational product.
- Request of any relevant regulatory agency.

# 5.8.2. Criteria for terminating the study at site

The Sponsor reserves the right to terminate the study at any given investigational site at any time after the study initiation if:

- ICH GCP regulations are not observed.
- Serious and continuous protocol deviations.
- The data generated are of poor quality.
- Changes in personnel or facilities that may adversely affect performance of the study (e.g. low rate of inclusion).

# 6. INVESTIGATIONAL TREATMENT

# 6.1. INVESTIGATIONAL MEDICINAL PRODUCT (IMP)

SOM3355 is bevantolol hydrochloride, a synthetic drug currently commercialized as a racemic mixture of S-bevantolol (-) and R-bevantolol (+) and used as antihypertensive drug. Bevantolol is approved and has been commercialized in Japan since 1995 as Calvan® by Nippon Chemiphar in the form of 100 mg film-coated tablets.

Bevantolol is a synthetic propanolamine that is 3-aminopropane-1,2-diol in which the hydrogen of the primary hydroxy group is substituted by 3-methylphenyl and one of the hydrogens attached to the nitrogen is substituted by 2-(3,4-dimethoxyphenyl) ethyl.

Chemical Name: Bevantolol HCl (racemate)

Molecular formula: C20H27NO4·HCl Molecular Weight: 381.897 g/mol

IUPAC Name:  $(\pm)$ -1-[(3,4-Dimethoxyphenethyl)amino]-3-(m-tolyloxy)-2-propanol

hydrochloride

CAS No: 59170-23-9

Chemical Structure:

(rac)- Bevantolol hydrochloride

In this clinical trial, the investigational medicinal product (IMP) i.e. SOM3355 (bevantolol hydrochloride) will be administered as capsules of 200 mg and 300 mg containing 2 or 3 film-coated 100 mg tablets of Calvan® (the commercial form of bevantolol) or matching capsules of placebo.

The active study drug used in the capsules is the commercial formulation of Calvan® in 100 mg film-coated tablets manufactured by Nippon Chemiphar, imported from Japan and released in Europe by the Contract Manufacturing Organization (CMO) Sharp Clinical Services Ltd, which is responsible for the encapsulation of the tablets and also manufactures the placebo matching capsules.

# Description of the 100 mg Calvan® tablets used:

# Composition:

- 100 mg of bevantolol hydrochloride per tablet
- Additives: lactose hydrate, microcrystalline cellulose, carmellose, hydroxypropylcellulose, hydrogenated oil, magnesium stearate, hypromellose, macrogol 6000, titanium oxide, and carnauba wax.

Calvan Tablets 100 Diameter: 8.5mm
Thickness: 3.2mm
Weight: 169.0mg

NCCE

# **Calvan Tablets 100**

Figure 2: Appearance and Details of Calvan® 100 mg Tablets

According to the SmPC, stability of the tablets are 39 months in blister packs (polyvinylchloride film, aluminum foil) or in sealed brown glass bottles at room temperature and under accelerated test (40°C-75%RH).

Expiration period: 3 years (according to stability test results).

As it is a really stable drug, no special storage conditions are required.

To ensure the blinding, the 100 mg Calvan® tablets will be over-encapsulated in hard gelatin capsules (Swedish orange DBcaps® AAel) in 2 different dosages: 200 mg and 300 mg.

To obtain the different dosages, capsules containing 200 mg (i.e. 2 tablets) and 300 mg (i.e. 3 tablets) of SOM3355, and capsules containing placebo will be prepared by the CMO.

Matching placebo capsules will have the same appearance as the active drug capsules (form, dimension, color, and taste) to ensure that neither the patient, nor the Investigator, nor members of the clinical staff know the identity of the study medication.

#### 6.2. PACKAGING AND LABELLING

The IMP will be packed in HDPE Duma Twist-Off 100 mL bottles containing 14 capsules, which corresponds to 1 week of treatment. Bottles will be labelled in different languages according to country specific directives and regulations and then delivered to the sites' pharmacies.

## **6.3.** MANAGEMENT AND STORAGE

The IMP requested via IWRS will be provided by the CMO to the sites' pharmacies, already packed in bottles and labelled, ready to be supplied to the patients.

The medication product does not require any special storage conditions, so it can be stored at room temperature and no temperature control is needed for shipments and site storage.

The medication will be stored in the sites' pharmacies until the study staff pick them up according to IWRS allocation for dispensation to patients.

All movements of study medication must be documented in an accountability log kept in the pharmacy service. Unused and returned study medication should be kept until the end of the study.

#### 6.4. STUDY DRUG DISPENSING

At each visit, the patient will be dispensed with the sufficient amount of IMP bottles: 1 bottle per week is needed, but additional bottles will be dispensed to secure any potential incident or any delay of the visits, i.e. 1 extra bottle will be added at some visits.

Apart from the IMP bottles, the investigator will give the patient the corresponding page of the Patient Diary, where the patient will register the time and date of all the medication intakes and any incidents.

During the following visit, the patient must return the Diary page completed and the bottles with any leftover medication or full or empty bottles to check treatment compliance and accountability.

#### 6.5. TREATMENT COMPLIANCE AND ACCOUNTABILITY

The Investigator or designated study staff is responsible for monitoring the patient's compliance with study medication during the trial. Compliance will be assessed by capsules count, i.e., evaluation of returned study medication (e.g., amount used/amount expected to be used in the interval between visits) and must be reviewed at every visit by interviewing the patient to determine if he/she is taking study medication as directed.

Compliance will be evaluated by calculating the number of capsules used (capsules dispensed minus capsules returned) divided by the expected number of capsules to be used. A patient will be deemed compliant if the patient has taken  $\geq 80\%$  but  $\leq 120\%$  of the expected tablets of study drug.

When the number of tablets used exceeds the number of expected tablets to be used, the Investigator must clarify the reason for this and in case of over dosage, this must be reported.

#### **6.6.** PROCEDURE FOR EMERGENCY INDIVIDUAL UNBLINDING

This study will be conducted in a double blind manner. Neither the patient nor the Investigator will know to which treatment a patient is randomized. The study blind should not be broken except in a medical emergency (where knowledge of the study drug received would affect the treatment of the emergency) or regulatory requirement (e.g., for SAEs or death [in Germany]). At that point, the Investigator may connect to the IWRS and have access to the treatment group for a specific patient.

The unblinding of a patient's treatment must be documented in the source documentation and in the patient's eCRF together with date and time, and the reason of unblinding and signed by investigator.

If possible, such emergencies should be discussed with the trial Medical Manager prior to disclosure of the treatment allocation. Should the code be broken, the Sponsor must be notified immediately.

## 7. STUDY ASSESSEMENTS

# 7.1. Unified Huntington's Disease Rating Scale (UHDRS®)

The standard clinical assessment tool in HD is the **Unified Huntington's Disease Rating Scale** (**UHDRS**®), developed by the Huntington Study Group to monitor disease progression in individual patients, and used in research and clinical practice to determine the efficacy of experimental therapies for the treatment of HD. It assesses 4 domains of clinical performance and capacity in HD: motor function, cognitive function, behavioral abnormalities, and functional capacity. The UHDRS® has undergone extensive reliability and validity testing and has demonstrated to be sensitive to detect longitudinal changes in manifest HD patients. It is used as a major outcome measure in controlled clinical trials (Huntington Study Group, 1996).

The entire UHDRS® is composed of 6 sections (Motor, Cognitive, Behavioral, Functional Assessment, Independence Scale, and Total Functional Capacity).

The motor section is made of 31 items including the assessment of chorea on 7 items (providing the TMC sub-score), dystonia, bradykinesia/rigidity, gait/balance and oculomotor function, and will be rated at each visit for efficacy assessment.

The functional domain comprises 3 sections, namely the total functional capacity (TFC), the functional assessment scale (FA), and the independence scale (IS).

In this study, **UHDRS**® **motor part will be used to assess efficacy outcomes at each visit**, and TFC and FA scales will be performed at baseline and at the end of the maintenance dose of study drug for safety assessment. The cognitive component and the behavioral assessment won't be used, and are replaced by other recommended scales for HD (Mestre et al, 2018).

At the inclusion, patients will be selected according to their functional status assessed by the TFC scoring the severity of HD and their functioning to exclude severe patients with TFC <7, and the severity of chorea symptoms assessed by the total chorea score that should be  $\geq 10$  at the inclusion.

The main efficacy assessment is focused on the choreic movements measured with TMC score included in the motor part of the UHDRS® as primary endpoint. Other sub-scores of the motor part of UHDRS® will also be considered such as TMS assessing overall motor function and the Gait sub-score and Dystonia sub-score.

#### 7.2. EFFICACY ASSESSMENTS

# 7.2.1. Total Maximal Chorea score (TMC) of the UHDRS®

The TMC score is part of the motor assessment of the UHDRS® consist of the sum of the seven body regions used to assess chorea including the face, oral-buccal-lingual region, trunk and each limb independently. Each territory is scored from 0 (normal findings) to 4 indicating severe abnormalities (0=absent, 1=slight/intermittent, 2=mild, 3=moderate/ common, 4=marked prolonged). The minimum TMC score is 0 (absent) and the maximal score is 28. A decrease in score indicates improvement in chorea.

This scale, which specifically targets a single motor feature in HD (chorea) and has been validated for this purpose, is more adequate in assessing for a specific symptomatic treatment indication.

TMC score will be assessed at each visit.

# 7.2.2. Total Motor Score (TMS) of the UHDRS®

The motor part of UHDRS® assessing the Total Motor Score is made of 31 items including chorea (TMC sub-score), dystonia, gait/balance, bradykinesia/rigidity, and oculomotor function. The items are rated from 0 to 4, with 0 indicating normal findings and 4 indicating severe abnormalities. The range of the **Total Motor Score (TMS)** is 0 to 124, with higher scores indicating more severe motor impairment.

TMS score will be assessed at each visit.

Sub-scores of gait and dystonia will also be analyzed as individual outcomes.

# 7.2.3. Clinical Global Impression (CGI) Scale

The CGI is a 7-point Likert Scale that asks the clinicians to rate, considering their total experience with this type of patients, the level of illness due to chorea at baseline on the illness severity ranging from normal (1) to extremely ill (7) (CGI-Severity), and after initiating therapy the overall global improvement (CGI-Change), since the initiation of study drug dosing, ranging from very much worse (7) to very much improved (1), to assess overall response to therapy by the clinician.

CGI-S will be assessed at the inclusion (Visit 1 at Day 0), and CGI-C at each following visit.

## 7.2.4. Patient Global Impression (PGI) Scale

The PGI is a 7-point Likert Scale that asks the patients to assess their HD symptoms at specific visits: at baseline (PGI-Severity) on the illness severity ranging from normal (1) to extremely ill (7), and after initiating therapy (PGI-Change), ranging from very much worse (7) to very much improved (1), to assess overall response to therapy. In general, patient-rated global measures of change have face validity and have been shown to correlate with disability for a number of chronic conditions.

PGI-S will be assessed at the inclusion (Visit 1 at Day 0), and PGI-C at each following visit.

#### 7.2.5. EO-5D-5L

EQ-5D-5L measuring quality of life is a validated self-report questionnaire developed by EuroQol Group. This scale is widely used in clinical trials, population studies and real-world clinical settings – and have proven to be valid, reliable and responsive in numerous conditions and populations. The EQ-5D-5L is used worldwide and has been translated into most major languages through a closely monitored translation process.

Aspects of life quality are assessed by measuring 5-item dimension as following: mobility, self-care, usual activities, pain/discomfort, and anxiety/depression, each dimension scored according to five response levels (no problems, slight problems, moderate problems, severe problems, and unable

to/extreme problems) coded from 1 to 5. The respondent is asked to indicate his/her health state by checking the box next to the most appropriate statement in each of the 5 dimensions.

In addition, the patients will use a visual analogue scale (VAS) to assess their own health state on a vertical scale where the extreme endpoints are labelled 'The best health you can imagine' scoring 100 and 'The worst health you can imagine' scoring 0. This information can be used as a quantitative measure of the patient's perception of their overall health.

EQ-5D-5L will be rated at the inclusion (Visit 1 at Day 0) and at the end of maintenance dose (Visit 5 at end of Week 10).

# 7.3. SAFETY ASSESSMENTS

# 7.3.1. Laboratory Assessments

Safety Laboratory tests (hematology, biochemistry) listed in Table 3 below will be performed at the screening visit (Visit 0), at the interim visit (Visit 3 at the end of Week 6), and at the end of maintenance dose (Visit 5 at end of Week 10). Blood samples for hematology and biochemistry should be obtained prior to study medication dosing. In total, approximately 10 mL blood should be drawn.

Safety laboratory samples will be analyzed via local laboratories. Safety laboratory tests are to be reviewed by the Investigator.

Abnormalities (e.g. AEs) will be defined as laboratory test results that are outside the reference range as defined by the normal range for laboratory test and clinically significant according to the Investigator's assessment.

**Table 3: Laboratory Parameters** 

Hematology				
Red blood cell count	Mean corpuscular hemoglobin	Reticulocytes		
Hematocrit Hemoglobin	Mean corpuscular volume Platelet count	White blood cell count with differential (neutrophils, lymphocytes, monocytes, eosinophils, basophils)		
Serum chemistry				
Alanine aminotransferase	Aspartate aminotransferase	Alkaline phosphatase		
Albumin	C-reactive protein	Calcium		
Total Protein	Creatine kinase (CPK)	Phosphate		
Bicarbonate	Creatinine	Chloride		
Bilirubin, direct and total	Urea	Potassium		
Gamma glutamyl transpeptidase	Glucose	Sodium		
Other				
Pregnancy test in women of childbearing potential				

#### 7.3.2. Physical Examination

Physical examination will be performed *at each visit*. Any significant change in each system class should be recorded.

## 7.3.3. Vital signs (Heart rate and Blood Pressure)

Blood pressure and heart rate must be measured in clinic at the beginning of each visit (before ECGs and/or blood sample collection) according to the European Society of Hypertension guidelines (Stergiou et al. 2021 ESH guidelines). Standardization for blood pressure measurements is necessary to obtain consistency of the collected data. Vital signs should be measured at each visit in the same conditions, with a validated and calibrated electronic device and using an adequate cuff for the arm circumference of the patient. The electronic device to be used for blood pressure measurement must be listed among the validated devices in the: https://www.stridebp.org website.

# Four sequential measures should be performed as follows:

First heart rate and blood pressure measurements should be taken after the patient has rested quietly in a comfortable sitting position for at least 5 minutes, his/her back and arm supported with the middle of the upper arm at heart level, legs uncrossed, and feet flat on the floor.

Orthostatic blood pressure and pulse will be assessed in the supine and standing positions according to the ESH guidelines. The patient should be in supine position for at least 5 minutes before the supine blood pressure and pulse are measured.

The patient will then move to the standing position. Standing blood pressure and pulse will be obtained after the patient has been in the standing position for 1 minute and 3 minutes. Register each measurement with the correct position/time. Ask the patient if he/she is experiencing any symptoms of light-headedness or dizziness.

A drop in BP of  $\geq$ 20 mm Hg, or in diastolic BP of  $\geq$ 10 mm Hg, or experiencing light-headedness or dizziness is considered abnormal.

All measurements will be recorded on the vital signs eCRF. Abnormal test results may be repeated at the discretion of the Investigator and must be reported on the corresponding eCRF.

## 7.3.4. Electrocardiograms (ECGs)

ECG will be performed according to the AHA/ACC recommendations for the standardization and interpretation of the ECG. All ECGs will be performed after at least 5 minutes' rest in a supine or semi-supine position. 12-lead ECGs to assess safety will be recorded at Screening Visit, inclusion visit (Visit 1), Visit 2, Visit 4, and Visit 6.

All ECG will be transferred by telemetry to the ECG central reading lab (Banook cardiabase) and ECG parameters (PR, QRS, QT, and QTcF) will be registered in the database and analyzed by a cardiologist. A report will be sent to the site within 48 hours after the visit. One paper version will be edited for the source document that can be examined by the Investigator during the visit.

At the inclusion, the ECG will be triplicated i.e. 3 successive records at 5 minutes of intervals and the average of all parameters will be calculated for baseline reference. This allows to have good quality for the reference ECG. Then the measurements of the 3 ECGs are averaged in a report.

#### 7.3.5. Columbia Suicide Severity Rating Scale (C-SSRS)

The C-SSRS is a questionnaire developed by multiple institutions, including Columbia University with NIMH support, used to assess suicide risk in trials of central nervous system active compounds. It is a semi-structured clinical interview that assesses suicidal ideation severity, suicidal ideation intensity, and suicidal behavior (Posner et al, 2011).

The C-SSRS is an interview performed by trained study personnel that should be done at baseline and at each visit during the study as outlined in the Schedule of activities to assess the status of the patient regarding suicide ideation and the risk of suicide attempt. The "Baseline/Screening" C-SSRS form provided at Screening collects the history of suicide attempts, while for subsequent visits the C-SSRS form termed "Since the Last Visit" should be used.

C-SSRS will be assessed at each visit.

## 7.3.6. Beck Depression Inventory (BDI)

The BDI scale is currently one of the most widely used instruments in both research and clinical practice for assessing depression, with good reliability and validity, which can be used to document changes brought by therapy. Created by [name] in 1961, and revised in 1996 (BDI-II) for more consistency with the revised DSMIV, it is a 21-question multiple-choice self-report inventory. The questionnaire is composed of items relating to symptoms of depression such as hopelessness and irritability, cognitions such as guilt or feelings of being punished, as well as physical symptoms such as fatigue, weight loss, and lack of interest in sex (Wang , 2013).

Each item has four possible degree of severity rated from 0 to 3, and the patient is asked to choose the one that is closest to how he/she feels. The 21 items are summed linearly to create a score which ranges from 0 to 63. It can be administered as an interview by the clinician or as a self-report instrument.

The suicide item #9 includes the following:

- 0. "I don't have any thoughts of killing myself."
- 1. "I have thoughts of killing myself, but I would not carry them out."
- 2. "I would like to kill myself."
- 3. "I would kill myself if I had the chance."

Total Score Levels of depression (Beck et al, 1988):

- 0 to 9: No depression or minimal depression
- 10 to 18: Mild to moderate depression
- 19 to 29: Moderate to severe depression
- 30 to 63: Severe depression

BDI will be assessed at each visit.

A total score of BDI-21 items  $\ge$ 30 or item 9 >0 results in an exclusion of the patient from further participation in the study.

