Exclusion criteria	Patients are excluded from the study if any of the following criteria apply:  1. Onset of HD symptoms prior to age of 21 years, corresponding to juvenile forms of HD.
	2. HD patients presenting rigid akinesia.
	3. Use of other vesicular monoamine transporter type 2 (VMAT2) inhibitors such as tetrabenazine, deutetrabenazine, or valbenazine within 3 months before enrollment, and at any time during the study period; and use of other antichoreic treatment such as any neuroleptic within 2 months or amantadine, memantine, riluzole within 1 month before enrollment and along the study.
	4. Patients who experienced severe depression or suicide attempt in the last 5 years.
	5. Severe untreated or under-treated psychiatric illness such as active suicidal ideation or behavior (BDI-21 item #9 >0 and active suicidal ideation in C-SSRS) or depression at screening and/or initiation visit (BDI-21 items total score >30); although patients taking authorized antidepressant therapy at a stable dose for at least 2 months and stabilized can be enrolled.
	6. Patients with a history of, or current, hypotension (SBP <110 mmHg), bradycardia (HR <50 bpm), or orthostatic hypotension as defined by the European Society of Hypertension (reduction in SBP ≥20 mmHg or in DBP ≥10 mmHg).
	7. Patients with hypertension already treated with more than 2 antihypertensive drugs.
	8. Other active clinically significant illness, including unstable cardiovascular disease, angina pectoris, congestive heart failure, pulmonary hypertension, peripheral arterial disease, history of pheochromocytoma, asthma, COPD, diabetic ketoacidosis or metabolic acidosis, or neoplastic pathology, which could interfere with the study conduct, or counter-indicate the study treatment, or to place the patient at risk during the trial, or compromise their study participation.
	9. Any significant serious abnormality in the electrocardiogram (ECG), e.g. recent myocardial infarction, significant sinus bradycardia (<50 bpm), atrioventricular block (grades I to III with PR >240msec), sinoatrial block, atrial sinus disease or prolonged QTc interval at screening (ECG

Bazett's corrected QT interval (QT  $/\sqrt{[HR/60]}$  >450 msec for males or >470 msec for females), or a known history of long QTc syndrome.

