#### 5.2. EXCLUSION CRITERIA

Patients are excluded from the study if any of the following criteria apply:

- 1. Onset of HD symptoms prior to age of 21 years, corresponding to juvenile forms of HD.
- 2. HD patients presenting rigid akinesia.
- 3. Use of other vesicular monoamine transporter type 2 (VMAT2) inhibitors such as tetrabenazine, deutetrabenazine, or valbenazine within 3 months before enrollment, and at any time during the study period; and use of other antichoreic treatment such as any neuroleptic within 2 months or amantadine, memantine, riluzole within 1 month before enrollment and along the study.
- 4. Patients who experienced severe depression or suicide attempt in the last 5 years.
- 5. Severe untreated or under-treated psychiatric illness such as active suicidal ideation or behavior (BDI-21 item #9 >0 and active suicidal ideation in C-SSRS) or depression at screening or baseline (BDI-21 items total score >30); although patients taking authorized antidepressant therapy at a stable dose for at least 2 months and stabilized can be enrolled.

- 6. Patients with a history of, or current, hypotension (SBP <110 mmHg) or bradycardia (HR <50 bpm), and patients with known orthostatic hypotension as defined by the European Society of Hypertension (reduction in SBP ≥20 mmHg or in DBP ≥10 mmHg).
- 7. Patients with hypertension already treated with more than 2 antihypertensive drugs.
- 8. Other active clinically significant illness, including unstable cardiovascular disease, angina pectoris, congestive heart failure, pulmonary hypertension, peripheral arterial disease, history of pheochromocytoma, asthma, COPD, diabetic ketoacidosis or metabolic acidosis, or neoplastic pathology, which could interfere with the study conduct, or counter-indicate the study treatment, or to place the patient at risk during the trial, or compromise their study participation.
- 9. Any significant serious abnormality in the electrocardiogram (ECG), e.g. recent myocardial infarction, severe sinus bradycardia (<50 bpm), atrioventricular block (grades I to III, with PR >240 msec), sinoatrial block, atrial sinus disease or prolonged QTc interval at screening (ECG Bazett's corrected QT interval (QT /√ [HR/60] >450 msec for males or >470 msec for females), or a known history of long QTc syndrome.

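### The depression and suicidality limits in the eligibility and withdrawal lists are looser than the removal rule in Protocol 7.3.6

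*Protocol*

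**What the plan says.** **Removal rule.** Protocol 7.3.6 has the BDI done at every visit. A total of 30 or more removes the patient, "or item 9 >0 results in an exclusion of the patient from further participation in the study". The same section bands the score as "30 to 63: Severe depression".

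**Entry list, total score.** Exclusion 5 in the synopsis reads "depression at screening and/or initiation visit (BDI-21 items total score >30", and in 5.2 "depression at screening or baseline (BDI-21 items total score >30". It ends with a proviso: "although patients taking authorized antidepressant therapy at a stable dose for at least 2 months and stabilized can be enrolled". Exclusion 4 separately bars severe depression or a suicide attempt within the past five years.

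**Entry list, suicidality.** Exclusion 5 gives the condition as "BDI-21 item #9 >0 and active suicidal ideation in C-SSRS", in the synopsis and in 5.2.

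**Withdrawal list.** Section 5.7 uses a total of 30 or more, and again item 9 above 0 together with active C-SSRS ideation.

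**Risk section.** Section 2.2.3 treats item 9 above 0, on its own, as excluding a patient at entry. It also calls for immediate withdrawal if suicide risk appears during the trial.

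**Instruments.** Of the BDI, 7.3.6 says "It can be administered as an interview by the clinician or as a self-report instrument". Section 7.3.5 says "The C-SSRS is an interview performed by trained study personnel".

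**The concern.** Section 3.1 singles out depression and suicidality among the safety objectives. At Visit 1 the investigator must recheck the inclusion and exclusion criteria (8.1.2), and on study the natural reference is the withdrawal list in 5.7. The stricter rule sits in the description of an instrument. A site working from the lists can enrol or keep a patient whom a site applying 7.3.6 would remove.

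Such a patient would be a deviation under Protocol 11.5 without breaching exclusion 5. The eligibility-violation row in SAP 2.3 would not pick the case up. Only the general deviation review, or the clause allowing further deviations to be identified at the meeting, could do so. SAP 4.10.8 describes BDI totals and item 9 but sets no limit, so it does not settle which rule holds.

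**Working it through.** No plan figure needs reproducing. The check sets the rules side by side and asks which patients they treat differently.

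| Place | When | BDI total | Item 9 |
|---|---|---|---|
| Synopsis, exclusion 5 | V0, V1 | >30 | >0 and active C-SSRS ideation |
| 5.2, exclusion 5 | V0, V1 | >30 | >0 and active C-SSRS ideation |
| 5.7 | on study | ≥30 | >0 and active C-SSRS ideation |
| 7.3.6 | every visit | ≥30 | >0 alone |
| 2.2.3 | entry | no number | >0 alone |

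The total is given as >30 in 2 places and ≥30 in 2. Item 9 is tied to the C-SSRS in 3 places and stands alone in 2.

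**Total score.**
- The scale has 21 items scored 0 to 3, so the range is 0 to 21 × 3 = 63, which is 64 possible totals.
- The rules >30 and ≥30 differ only at 30, so at 1 of 64 totals.
- There are 7 visits (V0 to V6), and exclusion 5 applies at V0 and V1, so at 2 of 7.
- After entry, 5.7 and 7.3.6 both use ≥30 and agree.
- At a total of 30 on V0 or V1, exclusion 5 is not met, 7.3.6 is met, and the protocol's own band calls the score severe.

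**Item 9.** Answers run from 0 to 3.

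| Item 9 | Active C-SSRS ideation | Listed trigger in 5.2 or 5.7 | 7.3.6 on item 9 |
|---|---|---|---|
| >0 | yes | met | met |
| >0 | no | not met | met |
| 0 | either | not met | not met |

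The rules part in the second row, at any of the 7 visits; 2.2.3 sides with 7.3.6 at entry. That row is a realistic one. The BDI may be self-completed while the C-SSRS is a staff interview, and an item 9 answer of 1 covers suicidal thoughts the patient would not act on.

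**Do the instructions contradict each other?** Sections 5.2 and 5.7 never require a patient to be enrolled or kept. Applying 7.3.6 throughout therefore breaches nothing. The fault is that the working lists omit the stricter limits.

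These counts describe the text. They are not frequencies, and the documents give nothing from which to estimate how many patients fall in either gap.

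**The case against.** The strongest reply is that a site following the whole protocol never goes wrong, because 7.3.6 governs and nothing forbids applying it. That is correct, and it limits the seriousness. It does not dispose of the point, because the rule protects patients only if sites apply it over the lists they check.

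The total-score gap is one value at entry, and exclusion 4 may catch some patients scoring 30. That also stands, but only in part: a questionnaire band is not a diagnosis, and exclusion 4 gives no BDI limit. The wording of exclusion 5 and of 5.7 is open, so an investigator may act on item 9 alone under either. That permits the stricter action without requiring it.

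One could instead weaken 7.3.6 and 2.2.3 to match the lists. That would be equally consistent, but it would relax a safety rule on a risk the protocol singles out. Aligning upward asks for nothing that 7.3.6 does not already demand.

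A reader might infer three stronger points, which the documents do not support:

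- **The antidepressant proviso lets in the whole severe range.** The proviso covers patients on a stable dose who are also stabilized, inside a criterion about untreated or under-treated illness. Reading it as overriding the numeric limit is strained.
- **The word *may* in 5.7 is a further conflict.** It is a general lead-in to an open list that also includes pregnancy, for which 5.4 gives a firm instruction to stop treatment. It does not contradict 7.3.6.
- **Active C-SSRS ideation alone should already trigger removal.** No section states that as a limit. Adding it would be an optional safety choice, not a correction.

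**Conclusion.** The inconsistency is real and should be fixed. It is a consistency and safety defect of limited extent: one BDI total (30) at V0 and V1, and, at any visit, patients with item 9 above 0 and no active C-SSRS ideation. The item 9 mismatch is the more substantial part, because it also affects decisions on study.

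This rests on three readings: that 7.3.6 applies at every visit, including V0 and V1, since it names no exception; that the joint condition in exclusion 5 and 5.7 means both parts; and that a BDI total of 30 does not by itself establish severe depression under exclusion 4. If the third reading is wrong, the total-score gap closes and the item 9 gap remains.

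A reader might go on to infer bias in the primary comparison. The documents give no basis for that, and none is claimed.

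**What to change.** Change the BDI limit from >30 to ≥30 in exclusion 5, in the synopsis and in 5.2. In the synopsis, 5.2 and 5.7, replace the joint item 9 and C-SSRS condition with the item 9 above 0 rule already in 2.2.3 and 7.3.6. Cross-refer 5.7 to 7.3.6, so that removal on these limits is not read as optional.

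The cost is a wording amendment and a letter to sites. Compared with 5.2 and 5.7 read alone, there may be a few more exclusions or withdrawals, and so slightly more missing primary data. None goes beyond what 7.3.6 already requires. No analysis method changes.

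The protocol planned a start in late 2021 and a one-year study; SAP 1.0 is dated 2024-07-12, and enrolment status is not stated. If enrolment is complete, flag two groups at the blinded data review: patients with a BDI total of 30 at V0 or V1, and patients with item 9 above 0 without active C-SSRS ideation who were enrolled or kept. This is one filter on data that SAP section 4 already lists by patient.
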